5.8.6.1 Breaking the Blind

The study drug blind will not be broken by the investigator or designee unless information concerning the study drug is necessary for the medical treatment of the subject. For unblinding a subject, the randomization information for unblinding can be obtained by contacting the dispensing pharmacist. The FDA or medical monitor must be notified immediately if the study drug blind is broken. The date, time, and reason that the blind was broken will be recorded in the source documents. If the blind is broken by the investigator or designee, the study drug must be stopped immediately, and the subject must be withdrawn from the study. Data or specimens already collected from subjects who discontinue prematurely and for whom the blind is broken will be made available for analysis if needed.

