5.5. Criteria for Subject Withdrawal

Subjects may withdraw from the study at any time at their own request, or they may be withdrawn by the investigator without the approval of the subject based on the investigator's clinical judgment. A subject is not required to provide a written request to withdraw from the study; however, a written request is required if a subject withdraws consent for his or her personal data to be used for study-related purposes.

A subject may be discontinued for any of the following reasons:

- AE: The subject has experienced an AE that, in the opinion of the investigator, requires early termination. The appropriate electronic case report form (eCRF) must be completed for each AE. If a subject is discontinued from the study due to an AE, the investigator is required to follow-up with the subject until the event resolves or becomes stable. If a subject dies during the study, the cause of death must be reported as a serious adverse event (SAE), with an outcome of death noted in the eCRF.
- Protocol Violation: The subject failed to meet protocol entry criteria or did not adhere to protocol requirements, and continued participation poses an unnecessary risk to the subject's health.
- Withdrawal by Subject: The subject (or other responsible individual [e.g., caregiver]) wishes to withdraw from the study in the absence of a medical need.

NOTE: Withdrawal due to an AE should not be recorded in the "voluntary withdrawal" category.

- Study Terminated by Sponsor: The sponsor, IRB, or other regulatory agency terminates the study.
- Pregnancy: The subject is found to be pregnant.

NOTE: If the subject is found to be pregnant, the subject must be withdrawn immediately. The pregnancy will be followed-up to term, and the outcome, including any premature termination will be recorded. All live births must be followed for a minimum of 30 days or until the first well-baby visit.

- Other.

NOTE: This category records withdrawals caused by an accidental or a medical emergency, unblinding, and other rare cases. The specific reason should be recorded in the comment space of the eCRF.

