5.5.1 Handling of Withdrawals

The investigator may terminate a subject's study participation at any time during the study when the subject meets the criteria described in Section 5.5. In addition, a subject may discontinue his or her participation without giving a reason at any time during the study. Subjects will be informed that their participation in the study is voluntary, that refusal to participate will involve no penalty or loss of benefits to which the subject is otherwise entitled, and that the subject may discontinue participation at any time without penalty or loss of benefits to which the subject is otherwise entitled.

Should a subject's participation be discontinued, the primary reason for termination must be recorded. In addition, efforts should be made to perform all procedures scheduled for the early termination visit. Any data and samples collected before subject withdrawal will become the property of the FDA.

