5.6.1.1 Compensation

Subjects will be offered payment for Screening; however, if the results of their alcohol and drug screening tests are positive, they will not be compensated. Subjects who complete the entire study will receive payment according to the schedule provided in the informed consent form. No special incentives are offered. Final payment will not be released until all follow-up procedures have been completed and accepted by the investigator.

If a subject chooses to withdraw from the study prematurely, he or she will only be compensated for completed days. If subjects are withdrawn for medical reasons or if the study is halted temporarily or permanently, the subjects will receive compensation proportional to the time spent in the study. No compensation will be provided if a subject is dismissed from the study for noncompliance (e.g., improper conduct, ingesting alcohol and/or drugs [including recreational drugs], tampering with the study drug, consuming any prohibited foods or beverages).

If subjects are required to stay in the clinic for a longer period for safety reasons, they will be compensated at a rate proportional to the entire compensation for the study. If a subject becomes ill or physically injured because of participation in this study, the subject will be referred for treatment.

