5.6.4 Discharge (or Early Termination)

The following procedures and assessments will be performed before the subject is discharged from the study (Day 63 or Day 123) or at early termination according to Table 9-1:

- Perform a serum pregnancy test (female subjects only)
- Record concomitant medications
- Monitor for AEs
- Perform clinical laboratory tests (hematology, serum chemistry, and urinalysis)
- Measure vital signs (blood pressure, heart rate, respiratory rate, and oral body temperature)
- Perform a safety 12-lead ECG
- Perform a complete physical examination
- Measure height, weight, and calculate body mass index
- Perform alcohol and drug screening (amphetamines, barbiturates, benzodiazepines, cannabinoids, cocaine, alcohol, opiates, phencyclidine, propoxyphene, and methadone)
- Collect a single PK blood sample (5 mL)
- Collect whole blood eosinophil blood sample (3.5 mL) for flow cytometry
- Collect whole blood (5 mL) and process for plasma for proteomic and small RNA transcriptomic analyses
- Collect urine (3-5 mL) for omic analysis (e.g., transcriptomics and/or metabolomics)
- Remove IV catheter (if applicable)
- Discharge subject from the study clinic after completion of all study procedures

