8.3.2 Protocol Violations and Deviations

Any significant protocol deviations that the investigator or study clinic staff believes are of major importance (e.g., incorrect randomizations, subject enrolled but not eligible) should be reported to the sponsor and the investigator's IRB as soon as possible.

Significant protocol deviations may include the following:

- Deviations from the inclusion/exclusion criteria that may affect subject safety
- Deviations (omission or delay) of safety monitoring procedures
- Deviations in the administration of the study drug
- Deviations in obtaining informed consent

All subjects who are enrolled and receive the study drug, regardless of whether they have a major protocol violation, must continue to be followed for safety for all follow-up study visits.

9. Appendices

Table 9-1: Schedule of Events by Time Point

	Screening	Check-in / Baseline	Treatment Period																				Enrolment Study	
			1	2	3	4	5	6	7	8	9	10	11	12	13	14	21	28	35	42	49	56	63	
Study Week																								
Study Day	-21 to -2	-1	Pre	1	1	1	1	1	1	1	1	1	1	1	1	1	2	3	4	5	6	7	8	9
Hour				0	0.5	1	2	3	4	6	9	12	16	24										
Visit		1		2		3																		
Outpatient visit																								
In House Residency		X																						
Informed Consent		X																						
Medical History		X																						
Targeted Physical Examination			X	X	X	X	X	X	X	X	X	X	X	X	X	X	X	X	X	X	X	X	X	
Comprehensive Physical Exam		X		X																				
Vital Signs		X		X		X	X																	
Telemetry				X	X	X	X	X																
12-Lead ECG		X		X																				
Clinical Chemistry and Hematology ¹		X		X																				
Urinalysis		X		X																				
HIV Ab, HbsAg, HepC Ab		X																						
SARS-CoV-2 Molecular Test																								
Urine Drug and Alcohol Screen		X		X																				
Pregnancy Test (females only) ²		X		X																				
FSH (females only)		X																						
Drug Administration																								
PK Sample (serum)					X		X	X	X	X	X	X	X	X	X	X	X	X	X	X	X	X	X	
Urine Sample Collection (PD)		X		X																				
Flow Cytometry Sample & Analysis		X		X																				
Genomics (puffy cell)				X																				
Proteomics & Small RNA					X		X	X	X	X	X	X	X	X	X	X	X	X	X	X	X	X	X	
Transcriptomics (plasma)						X	X	X	X	X	X	X	X	X	X	X	X	X	X	X	X	X	X	
Concomitant Medications						X	X	X	X	X	X	X	X	X	X	X	X	X	X	X	X	X	X	
Adverse Events						X	X	X	X	X	X	X	X	X	X	X	X	X	X	X	X	X	X	

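### Mandatory withdrawal after unblinding (Protocol 5.8.6.1) stops no drug once the single dose is given, but ends PK/PD sampling and new adverse event recording, and can end safety visits

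*Protocol*

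**What the plan says.** **Unblinding.** Protocol 5.8.6.1 allows the investigator or designee to break the blind only when the subject's medical treatment needs it. If that happens, "the study drug must be stopped immediately, and the subject must be withdrawn from the study". No exception is given. Data and specimens already in hand stay available for analysis.

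**Withdrawal.** Section 5.5 is mostly permissive: "A subject may be discontinued for any of the following reasons". Its note to the last category, Other, says: "This category records withdrawals caused by an accidental or a medical emergency, unblinding, and other rare cases". Pregnancy is the other mandatory case there, and it has its own follow-up rule.

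**After withdrawal.** Section 5.6.4 lists one set of procedures, "performed before the subject is discharged from the study (Day 63 or Day 123) or at early termination", with one PK sample and one eosinophil sample. Section 5.5.1 says "efforts should be made to perform all procedures scheduled for the early termination visit". Section 5.1.2 and the synopsis are firmer and say that the end-of-study procedures will be done. Under 5.7.4.1.2, adverse event recording runs to discharge or early termination.

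**Safety visits.** Section 8.3.2, on deviations, says that all enrolled and dosed subjects, "regardless of whether they have a major protocol violation, must continue to be followed for safety for all follow-up study visits".

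**Analysis.** SAP section 5 leaves subjects who stop before their assigned end-of-study day out of the PK and PD parameter summaries.

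**The concern.** A stop-and-withdraw rule suits a trial with repeated dosing, where staying in means more drug. Here there is one dose on Day 1. For a subject already dosed, all that is left of the rule is the end of observation, and it applies to someone who has just needed medical care.

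Two things are at stake. The first is safety information: new events after withdrawal are not recorded, and a site that follows 5.8.6.1 could reasonably cancel the remaining visits. The second is primary-endpoint data. A subject who could have completed sampling becomes an early-termination subject and drops out of the eosinophil summaries.

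The blind protects little in return. The endpoint is a flow cytometry count, route is open, and under 5.8.6 staff learn each subject's end-of-study day when confinement ends.

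**Working it through.** The plan states no figure on this point, so the check compares the texts and counts the schedule.

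**1. What drug is left to stop?** The synopsis gives one dose per subject and an infusion of at most 30 minutes. Sections 5.6.3.1 and 5.8.3.1 allow randomization on Day -1.
- Before dosing: the rule prevents dosing. It does useful work.
- During an infusion: it stops the infusion. Also useful.
- After the injection or infusion: nothing remains to stop.

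**2. What sampling is lost?** Post-dose eosinophil samples come from Protocol 5.7.2.1.1. SAP Attachment A shows that the 24-hour and Day 2 samples are the same.
- In house, Days 2 to 14: 13
- Weekly, Days 21 to 63: 7
- Days 93 and 123, groups C, D, G, H, I only: 2
- Totals: 13 + 7 = 20, or 13 + 7 + 2 = 22

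Outpatient visits are 7 or 9, which agrees with the maximum of 9 in Protocol 5.1. Samples still to come, if the blind is broken after that day's sample:

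| Day of unblinding | Groups A, B, E, F | Groups C, D, G, H, I |
|---|---|---|
| 1 | 13 + 7 = 20 | 13 + 9 = 22 |
| 7 | 7 + 7 = 14 | 7 + 9 = 16 |
| 14 | 7 | 9 |

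In each case one early-termination sample takes their place.

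**3. What safety observation is lost?** Recording of new adverse events ends at early termination (5.7.4.1.2). For visits, 5.8.6.1 requires withdrawal and 5.6.4 gives a withdrawn subject one closing set of procedures, while 8.3.2 can be read as requiring every safety visit for any dosed subject. Section 8.3.2 does not say whether it reaches withdrawn subjects, and neither section refers to the other. The visits may therefore be lost, but the text does not settle it. The delayed hypersensitivity in 5.1.3 is described for mepolizumab, with onset over days, so the days that matter most are those left in house.

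**4. Effect on precision.** Assume one event in an arm and no replacement, so n goes from 8 to 7.
- Standard error of the arm mean: sqrt(8/7) = 1.069, a rise of 6.9%.
- Relative standard error of the arm SD (normal approximation), 1/sqrt(2(n − 1)): 1/sqrt(14) = 26.7% becomes 1/sqrt(12) = 28.9%.
- 90% confidence half-width in SD units, variance pooled over nine arms with one covariate (an assumption about the ANCOVA in Protocol 5.9.6.1): t(0.95, 62)/sqrt(8) = 0.590 becomes t(0.95, 61)/sqrt(7) = 0.631, a ratio of 1.069.
- The same with each arm's own variance: t(0.95, 7)/sqrt(8) = 0.670 becomes t(0.95, 6)/sqrt(7) = 0.734, a ratio of 1.096.

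SAP 7.3.1 plans descriptive PD summaries without a confidence interval.

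**5. How often?** The documents give no frequency. Route is not blinded, and by each route 32 of 32 + 4 = 36 subjects (89%) get active drug, so treating staff will seldom need the code.

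**The case against.** The strongest reply is that the subject is already well protected. Read literally, 8.3.2 keeps the safety visits. Closing procedures are firmly required by 5.1.2, so the softer wording of 5.5.1 is not the whole rule. For an adverse event that leads to discontinuation, "the investigator is required to follow-up with the subject until the event resolves or becomes stable". Under 5.7.4.1.2, possibly or probably related events are followed to resolution or stability, and serious events to resolution. Section 5.6.1.1 foresees the case "If subjects are required to stay in the clinic for a longer period for safety reasons". Section 5.5.2 allows up to 14 replacements. A subject treated for a medical event may also receive medication that disturbs leukocyte counts, so some PD data could be lost anyway.

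All of this stands, and it makes the point small. A reader might infer that an ill subject is left without safety oversight; these provisions rule that out. They do not restore the scheduled PK/PD sampling or the recording of new, separate events. A replacement restores n only by dosing another healthy volunteer, who under 5.1.3 cannot benefit.

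The reply also limits the remedy. Simply deleting the rule would remove its useful effect before dosing and during an infusion, would let a partly dosed subject into the summaries, and could appear to override the right to leave.

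**Conclusion.** The point holds in limited form. After dosing is complete, mandatory withdrawal stops no drug. It replaces up to 20 or 22 eosinophil samples with one, ends recording of new adverse events, and removes the subject from the PK/PD summaries. It can end scheduled safety visits, depending on how a site reads 8.3.2.

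A reader might take 5.8.6.1 and 8.3.2 as a flat contradiction. The text supports only an unresolved ambiguity, because the latter sits in the deviations section and is silent on withdrawn subjects. A reader might also infer biased results. Nothing in the documents links code-breaking to the eosinophil outcome, and no bias is claimed.

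Severity is minor. The sample counts at Day 1 are the worst case, and the precision figures rest on one unreplaced event in one arm.

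**What to change.** Replace the withdrawal sentence in Protocol 5.8.6.1 with:

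> If the blind is broken before dosing, the subject is not dosed and is withdrawn. If it is broken during an infusion, the infusion is stopped immediately. Unblinding after any study drug has been given does not by itself require withdrawal: unless the subject withdraws consent or the investigator judges otherwise on medical grounds, safety visits and AE recording (see 8.3.2) and PK/PD sampling continue to the assigned end-of-study day.

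In the 5.5 note, limit unblinding to unblinding before dosing.

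In the SAP, make two additions. Leave partly dosed subjects out of the dose-group PK/PD summaries. Flag eosinophil values taken after medication known to affect leukocyte counts, and omit for that subject any PD parameter that uses them; dropping only the late values would leave a truncated AUEC. A fully dosed, unblinded subject who completes follow-up needs no special rule, since SAP section 5 excludes only those who stop early.

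The cost is a few sentences in two documents, with no visit or sample beyond those already scheduled. The one small downside is that rescue medication may affect some PD values, which then need flagging.

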5.8.7 Treatment Compliance

At Screening, as part of the inclusion criteria, it will be confirmed that subjects are able to comply with the protocol-defined procedure of injecting subcutaneous or receiving intravenous study drug. All doses of the study drugs will be administered in the study clinic either under direct observation of, or administered by, clinic personnel and recorded in the eCRF. If a subject vomits after dosing, the event will be documented as an AE. The decision to replace any subject who vomits after dosing will be made as described in Section 5.5.2.

5.8.8 Prior and Concomitant Medications

Subjects are prohibited from using any prescription or nonprescription drugs (including aspirin or non-steroidal anti-inflammatory drugs [NSAIDs] and excluding oral contraceptives and acetaminophen) within 14 days or 5 half-lives (whichever is longer), or complementary and alternative medicines within 28 days before the first dose of study drug.

Subjects are also prohibited from currently participating in another clinical study of an investigational drug and may not have been treated with any investigational drug within 30 days or 5 half-lives (whichever is longer) of the compound.

Subjects must be instructed not to take any medications, including over-the-counter products, without first consulting with the investigator.

5.8.9 Subject Restrictions

Subjects are not allowed to use nicotine-containing products (e.g., cigarettes, cigars, chewing tobacco, snuff) within 6 weeks before Screening. In addition, subjects are not allowed to ingest alcohol, xanthine-containing products (e.g., tea, coffee, chocolate, cola), caffeine, grapefruit, or grapefruit juice for 48 hours before dosing and throughout the study. Subjects are not allowed to use aspirin or NSAIDs within 14 days before the first

dose of study drug. Subjects will be asked if they have used any of these substances and their responses will be recorded on the eCRF.

Subjects must be able to tolerate a controlled, quiet study conduct environment, including avoidance of music, television, movies, games, and activities that may cause excitement, emotional tension, or arousal during prespecified times (e.g., before and during ECG extraction windows) throughout the duration of the study.

Subjects must be willing to comply with study rules, including the meal schedule, attempting to void at specified times (e.g., before ECG extraction windows), and blood draws.

Standardized meals will be served at consistent times relative to dosing, and no food or fluids will be served containing caffeine. Outside of meal times, the subjects will only be allowed to intake water, which will be available ad libitum.

5.9. Statistical Methods

5.9.1 Sample Size

Up to 86 healthy subjects will be enrolled (including 14 potential replacement subjects). Subjects will be randomized to one of 9 different active treatment arms (i.e. 8 per treatment arm) and 8 will be randomized to placebo. This sample size was determined empirically based on general sample size requirements for estimating values and variability of PD and PK/PD characteristics that can be used to inform the study design and sample size of future biosimilarity studies.

5.9.2 Analysis Populations

The PD and PK populations will include all subjects who receive study drug and have at least 1 estimable PD or PK parameter, respectively, after dosing.

5.9.3 General Statistical Considerations

All data will be presented in data listings. Data from subjects excluded from an analysis population will be presented in the data listings but not included in the calculation of summary statistics. Demographic and baseline characteristics will be summarized overall and by treatment for all subjects.

5.9.4 Subject Disposition

The number of subjects who enroll in the study and the number and percentage of subjects who complete each assessment will be presented. The frequency and percentage of subjects who withdraw or discontinue from the study and the reason for withdrawal or discontinuation will be summarized.

5.9.5 Demographics and Baseline Characteristics

Descriptive statistics will be used to summarize demographic and baseline subject characteristics. For continuous variables, the mean, median, standard deviation (SD), minimum, and maximum values will be reported. For categorical (nominal) variables, the number and percentage of subjects (or observations) will be reported.

5.9.6 Primary Analysis

5.9.6.1 Pharmacodynamics

Peripheral blood eosinophils_AUEC will be calculated for each subject. For each dose, separate intervals will be used for the AUEC assessment to truncate noise introduced from baseline fluctuations. Maximum decrease from baseline will be determined from all sampled timepoints. For both assessments and biomarkers, measures will be log-transformed and utilize an ANCOVA approach for calculating geometric means and 90% confidence intervals for each treatment. PD parameters of mepolizumab and reslizumab will be listed and summarized using descriptive statistics (n, geometric mean, coefficient of variation, minimum, median, and maximum).

Separate population PD analyses will be conducted using nonlinear mixed effect modeling with NONMEM. AUECs calculated for each subject from all doses for a drug and placebo patient will be combined and evaluated assuming a saturating E_{max} relationship to characterize system parameters such as E_{max} and EC_{50} .

5.9.6.2 Pharmacokinetics

C_{max} and AUC are the primary PK parameters of interest in PK similarity studies with a subcutaneous drug administration. These and additional PK parameters will be determined for each subject using non-compartmental methods. All parameters will be reported with standard descriptive statistics including the geometric mean and coefficient of variation. Calculation of PK parameters will be performed using actual sampling times.

5.9.7 Additional Analyses

5.9.7.1 Proteomics and small RNA Transcriptomics Analysis

A combination of differential expression testing of signals analysis, and clustering techniques will be used demonstrate subject response to each product. Differentially expressed plasma proteins and small RNAs will be identified using a 10% false discovery rate. Following technical and independent validation of the most promising or top 1% biomarker(s), dose- and exposure-response analysis will be performed as described above for the primary biomarker(s). The AUEC change along with maximal effect at a single time point for a promising biomarker(s) will also be calculated. The values, variability

and characteristics of the proteomic-array-based biomarkers will be compared to the traditional biomarker analysis outlined above. Based on proteomic and small RNA transcriptomic findings, the potential for a composite of relevant biomarkers to demonstrate PD similarity will also be evaluated. Additional details regarding the statistical methods for the proteomic and small RNA transcriptomic analyses will be described in a separate protocol.

